4.1. Efficacy Populations

The analysis populations for efficacy analyses include cancer specific populations as defined in [Section 4](#). Only patients who received at least one dose of IMMU-132 will be included in the analysis.

CCI

CCI

For other cancer-specific analysis populations, efficacy analysis and listings will be conducted where applicable. No per-protocol populations or sensitivity analyses are planned for cancer types other than mTNBC.

Data listing will in general be performed on the Overall Safety Population and where applicable, also on the cancer specific analysis population.

4.2. Safety Populations

For the purposes of summarizing safety data, there will be 4 populations, as follows:

- Target mTNBC Population, as defined in [Section 4](#).
- Metastatic, non-triple-negative breast cancer (mBC) Population, as defined in [Section 4](#).
- Metastatic Urothelial cancer including urinary bladder (mUC) Population, as defined in [Section 4](#).
- Overall Safety Population, as defined in [Section 4](#) which includes all patients regardless of cancer type, regardless of number of prior cancer therapies, and regardless of IMMU-132 dose as long as the patient received at least 1 dose of IMMU-132.

4.3. Per-Protocol Population

The Per-Protocol Population is defined as the subset of Target mTNBC patients who received at least 1 cycle of IMMU-132 and had available data from at least 1 response assessment. The Per-Protocol Population is specific to the mTNBC patients and mainly used for sensitivity analyses of efficacy, and no other cancer specific populations has a similarly defined per-protocol population.

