During the study, imaging was performed at baseline (ie, within 4 weeks of study entry) and thereafter in 8 weekly intervals from the start of treatment onwards, with confirmatory CT/MRI scans obtained 4 to 6 weeks after an initial partial response (PR) or complete response (CR), until permanent treatment discontinuation. Response assessment was performed according to Response Evaluation Criteria in Solid Tumors (RECIST) version 1.1. Response assessment was performed locally, but independent central review (ICR) of the tumor scans was additionally obtained for mTNBC patients who had at least 2 prior therapies for metastatic disease, were being treated at the 10 mg/kg dose level, and whose local scans demonstrated at least 20% decrease. ICR of tumor scans was performed by Intrinsic Imaging (Bolton, Massachusetts; San Antonio, Texas, US). The details of the independent review were provided in an imaging charter for the study.

After treatment discontinuation, patients were to be followed until resolution or stabilization of any treatment-related AEs. All patients were followed for survival every month, which may be by telephone with patient or caregiver.

CCI

The safety of patients is assessed based on occurrence of AEs, clinical laboratory assessments, vital signs, and ECGs.

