4. ANALYSIS POPULATIONS

Given that this study was conducted as a Phase I/Phase II and included a diverse population comprised of patients with different tumor types, it is necessary to define specific patient populations. The following sections outline the populations to be included for the evaluation of efficacy and safety. The patient populations to be used are:

- Target mTNBC Population: Patients with relapsed/refractory mTNBC who have received at least 2 prior therapies for metastatic disease and who received IMMU-132 at a dose of 10 mg/kg.
- Per-Protocol (PP) Population (specific to the Target mTNBC Population): This will include patients of the Target mTNBC Population who received at least 1 complete cycle of IMMU-132 and had data available from at least 1 response assessment.
- Overall Safety Population: This will include all patients who received at least 1 dose of IMMU-132, irrespective of dose, tumor type, or number of prior therapies.

At the time of final SAP (version 3.0), the following patient populations are added for safety and efficacy analyses:

- Metastatic, non-triple-negative breast cancer (mBC) Population: This will include all patients with hormone receptor-positive/human epidermal growth factor receptor 2-negative (HR+/HER2-) metastatic breast cancer (mBC) who progressed on at least 1 prior hormonal therapy in the metastatic setting and who received at least 1 dose of IMMU-132 at a dose of 10 mg/kg.
- Metastatic Urothelial cancer including urinary bladder (mUC) Population: This will include all mUC patients who had relapsed after or were refractory to at least 1 prior standard therapeutic regimen and who received at least 1 dose of IMMU-132 at a dose of 10 mg/kg.

And the following patient populations are added for limited efficacy analyses:

- Small-cell lung cancer (SCLC) Population: This will include all SCLC patients as enrolled in the study in accordance with the eligibility criteria and who received at least 1 dose of IMMU-132.
- Non-small-cell lung cancer (NSCLC) Population: This will include all NSCLC patients as enrolled in the study in accordance with the eligibility criteria and who received at least 1 dose of IMMU-132.
- Colorectal (CRC) Population: This will include all CRC patients as enrolled in the study in accordance with the eligibility criteria and who received at least 1 dose of IMMU-132.

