6.4. Progression-Free Survival

Progression-free survival is defined as the interval from the first dose start date to the date of disease progression defined as documented PD or death from any cause, whichever occurs first. Death was considered an end point only while the patient was on study and receiving treatment or undergoing response assessments. Patients otherwise without adequate response assessments or without radiologic evidence of progression were censored. Clinical PD was not considered as a PFS event. $PFS = (\text{Earliest Date of Disease Progression/ Death} - \text{First Dose Start Date} + 1) / 30.4375$.

The approach regarding handling of assessments, dates, and censoring presented in [Table 3](#) is based upon RECIST1.1 guidelines ([Eisenhauer et al., EJC, 2009](#)). **CCI**

[figure not shown]

Table 3: Guidelines for Response Assessment and Censoring for Analysis of Progression-Free Survival

Guidelines for Progression Assessment and Censoring for Analysis of PFS		
Case	Outcome	Date of Event/Censoring¹
No adequate response assessment after start of treatment		
Died prior to second scheduled assessment	PD	Date of death
Did not die prior to second scheduled assessment	Censor	Date of first dose
Continued study until objective PD or death		
At scheduled assessment	PD	Date of objective PD
Between scheduled assessments	PD	Date of objective PD or death
After missing 2 or more scheduled assessments	Censor	Date of last adequate response assessment before missed ones
Continued scheduled response assessments without objective PD or death		
Discontinued for undocumented PD, toxicity, other reasons	Censor	Date of last adequate response assessment
Lost to follow-up	Censor	Date of last adequate response assessment
Initiated other treatment	Censor	Date of last adequate response assessment prior to starting other treatment
No objective PD at final assessment	Censor	Date of last adequate response assessment

Abbreviations: CT = Computed tomography, MRI = Magnetic resonance imaging, PD = Progressive disease, PFS = Progression-free survival.

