6.5. Overall Survival

Overall survival is defined as the time from the date of the first dose start date to the date of death due to any cause. Patients without documentation of death at the time of the data cutoff for analysis will be censored at the date the patient was last known to be alive or the data cutoff date, whichever is earlier. The last known alive date is the last record in the study database. This date may be the maximum of the last visit date or last contact date, including telephone follow-up where the patient is known to be alive.

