6.9. Sensitivity Analyses

CCI

Analyses based on the Per-Protocol Population will be performed for ORR, PFS, and OS for the Target mTNBC Population.

Sensitivity analyses will only be conducted for the Target mTNBC Population, but not planned for other cancer-specific analysis population.

CCI

CCI

CCI

CCI

CCI

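### Per-Protocol OS and PFS are timed from first dose in patients selected on later events, so they are expected to come out too high and are weak evidence of robustness

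*SAP*

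**What the plan says.** SAP 4.3 defines the PP Population as Target mTNBC patients who "received at least 1 cycle of IMMU-132 and had available data from at least 1 response assessment". SAP 4 words the same set slightly differently: "received at least 1 complete cycle of IMMU-132 and had data available from at least 1 response assessment". SAP 4.3 says the set serves mainly for sensitivity analyses of efficacy.

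The endpoints are set in SAP 6.9: "Analyses based on the Per-Protocol Population will be performed for ORR, PFS, and OS for the Target mTNBC Population". Table 1 (SAP 4.4) lists the same three for the PP column.

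Neither time-to-event definition changes for this set. In SAP 6.4, "Progression-free survival is defined as the interval from the first dose start date to the date of disease progression". In SAP 6.5, OS is "the time from the date of the first dose start date to the date of death due to any cause". SAP 3.1 places scans at baseline and "thereafter in 8 weekly intervals from the start of treatment onwards". The readable text gives no landmark, delayed entry or other time origin for the PP analyses.

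The main efficacy analysis requires only one dose (SAP 4.1). Table 3 (SAP 6.4) counts a death before the second scheduled assessment, in a patient with no adequate assessment, as a PFS event at the date of death. A patient with no adequate assessment who did not die in that period is censored at first dose.

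**The concern.** A patient must normally live about eight weeks to supply response-assessment data, and those weeks are then counted as survival time. Early deaths without a scan count against the drug in the Target mTNBC Population and are absent from the PP set. This is immortal-time bias.

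What is at stake is the value of the sensitivity analysis. It should be able to challenge the main result. This one is expected to equal or exceed it, so a reader who sees similar or better PP medians could take that as support it does not give.

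**Working it through.** The readable text gives no PP sample size, number of exclusions, median OS or median PFS, so there is no plan figure to reproduce. The medians and dropped fractions below are assumptions used to show a range.

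**Inputs from the documents**
- First scheduled scan at 8 weeks, or 56 days (SAP 3.1).
- 30.4375 days per month (SAP 6.4).
- Target mTNBC Population of 108, all with at least 4 months of follow-up (SAP 4).

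**Step 1: the guaranteed period.** 56 / 30.4375 = 1.84 months. This is approximate. Study windows are nominally ±10% (50.4 to 61.6 days), and the protocol allows additional scans at the physician's discretion.

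**Step 2: who is dropped.** Four months is 4 × 30.4375 / 7 = 17.4 weeks, so the data cut-off does not explain a missing week-8 scan. The remaining reasons are mainly death, stopping treatment, or a missed scan. The first two are related to prognosis.

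**Step 3: OS by fraction dropped.** If a fraction q of patients is dropped and all of them are early deaths, then after the first scan S_PP(t) = S(t) / (1 − q). With exponential OS and median M, the PP median rises by M × [−ln(1 − q)] / ln 2.

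| q | Patients of 108 | Shift, M = 6 months | Shift, M = 12 months |
|---|---|---|---|
| 2% | about 2 | +0.17 | +0.35 |
| 5% | about 5 | +0.44 | +0.89 |
| 10% | about 11 | +0.91 | +1.82 |

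**Step 4: upper end for OS.** Suppose every first scan is on day 56 and every earlier death is dropped. Then q = 1 − 2^(−1.84/M), and the PP median is M + 1.84.

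| M (months) | Dead before week 8 | Patients of 108 | PP median | 12-month OS, Target to PP |
|---|---|---|---|---|
| 6 | 19.1% | 21 | 7.84 | 25.0% to 30.9% |
| 9 | 13.2% | 14 | 10.84 | 39.7% to 45.7% |
| 12 | 10.1% | 11 | 13.84 | 50.0% to 55.6% |
| 18 | 6.8% | 7 | 19.84 | 63.0% to 67.6% |

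If only half of those early deaths lack an assessment, the shift is about 0.9 months for M between 6 and 12.

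**Step 5: PFS.** Patients censored at first dose under Table 3 add no time at risk, so removing them leaves the Kaplan-Meier PFS curve unchanged. Patients who progress at the first scan stay in the PP set if they had a cycle. The upward effect therefore comes mainly from deaths before any assessment. If a fraction q dies in that way, and progression is otherwise found only at 8-weekly scans, PP exceeds Target by q × S_PP(t). Assume a latent median m of 3 to 8 months and q of 3% to 10%:
- Just after the first scan, S_PP = 2^(−1.84/m). The excess runs from 0.03 × 0.654 = 2.0 points to 0.10 × 0.853 = 8.5 points.
- At 6 months the last scan was at 3 × 1.84 = 5.52 months. The excess runs from 0.03 × 0.279 = 0.8 points to 0.10 × 0.620 = 6.2 points.

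In months, the step 3 formula scales with the median. At q = 5% and m = 5.5, the underlying PFS shift is 5.5 × 0.0740 = 0.41 months, against 0.89 for OS with M = 12.

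**The case against.** Three stronger readings are tempting, and the documents do not support them.

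- **That the PP analysis can only move the estimates upward.** The PP set also drops patients with less than one cycle, and patients alive without a scan, however long they live. The protocol keeps patients who stop for toxicity in follow-up until progression and follows all patients for survival. Someone who stopped after one dose and lived long is lost from the PP set, which lowers PP OS. Upward is the expected net direction, not a certainty.
- **That the patients Table 3 counts as early deaths are exactly those removed.** Table 3 turns on having no adequate assessment, which excludes those recorded as not assessed or not evaluable. The PP definition asks only for available assessment data. A patient with one not-evaluable scan who then dies early could be a Table 3 event and still be in the PP set.
- **That the bias is 1.84 months.** That is the upper-end case in step 4. Entry required ECOG 0 or 1 and expected survival of at least 6 months, so deaths before week 8 may be few and the shift near zero.

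Other points limit the consequence. ORR is the primary endpoint, no hypothesis is tested (SAP 6), and Table 1 lists a separate row of sensitivity analyses in the full Target population. Protocol 10.4 defines its own efficacy population by essentially the PP criteria, so the PP results serve as a link to the protocol. Parts of SAP 4.1, 6.9 and 11 are redacted, so a landmark rule there cannot be ruled out. All of this stands. None of it removes the mismatch between the selection and the time origin in the readable definitions.

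**Conclusion.** The point holds as an expected upward bias in PP OS, with a smaller one in PP PFS. Under exponential OS, the shift in the median runs from near 0 to about 1.8 months, depending on how many of the 108 are dropped as early deaths. The documents do not give that number. A reader might infer that the main mTNBC result is inflated too. It is not, because that analysis includes every Target patient with at least one dose. The other tumour cohorts have no PP set. The consequence is that agreement between PP and Target OS or PFS should not be read as evidence of robustness. It is worth correcting because the correction is cheap.

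**What to change.** In SAP 6.9:

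1. **PP OS:** analyse from a fixed landmark, for example week 8, in patients who are alive and meet both criteria by then. Alternatively, use delayed entry at the date both criteria are met. A landmark at day 62 would include first scans within the nominal window (56 × 1.1 = 61.6 days). In the exponential case with all first scans at week 8, restarting the clock there takes the 1.84 months back off (13.84 to 12 months).
2. **PFS:** rely on the Target mTNBC Population, or use a landmark among patients alive and progression-free at that time. Do not use delayed entry at the scan date, because progression found on that scan would coincide with entry.
3. **If PP PFS and OS from first dose are kept** because Protocol 10.4 defines the same population, label them as conditional on surviving to assessment and do not present them as a robustness check. Report the number excluded, with reasons and vital status. Simply deleting them is less attractive, since SAP 9 shows that analyses have already been run on the 30 June 2017 cut-off and a planned result would disappear afterwards.
4. **PP ORR:** keep as planned.
5. Use one wording for the cycle requirement in SAP 4 and 4.3.

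The cost is a short addition to the SAP and a little extra analysis, with no new data. The PP estimates will probably look slightly less favourable, and landmark results must be read as conditional on reaching the landmark.

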4.4. Analyses Population Overview

Analysis populations will be summarized in this study for relevant safety and efficacy endpoint. CCI [REDACTED] an overview of the analyses conducted is shown in [Table 1](#). At the time of final analyses to support CSR, requisite analyses CCI [REDACTED] for the Target mTNBC Population will be repeated based on the updated data based on the final DBL data cut-off date (the sample size of the Target mTNBC Population still remained the same in the updated data). In addition, additional analyses will be conducted for analysis populations other than mTNBC, along with analyses for the Overall Safety Population, an overview of the analyses is shown in [Table 2](#).

Table 1: Overview of Analyses and Populations CCI

	Target mTNBC Population	Overall Safety Population (N=420 CCI)	Per-Protocol Population
Disposition	X	X	
Demographics	X	X	
Prior anticancer therapy	X	X	
Concomitant medication and medical history	X	X	
Efficacy (ORR, PFS, OS, DOR, TTR)	X		X (only ORR; PFS; OS)
Sensitivity efficacy (ORR, PFS, OS)	X		
Exposure	X	X	
AEs	X	X	
Deaths	X	X	
Laboratory	X	X	
Vital signs	X	X	
ECG	X	X	
Subgroups efficacy	X		
Subgroups exposure	X	X	
Subgroups safety	X	X	
Major protocol deviations	X	X	

Abbreviations: AE = Adverse event, DOR = Duration of response, ECG = Electrocardiogram, mTNBC = Metastatic Triple Negative Breast Cancer, ORR = Objective response rate, OS = Overall survival, PFS = Progression-free survival, TTR = Time to response.

Table 2: Overview of Analyses and Populations for Final Analyses

	mBC	mUC	SCLC, NSCLC, CRC, EGC, EMC, PDC	Overall Safety Population (N=approximately 495 at final DBL)
Disposition	X	X		X
Demographics	X	X		X
Prior anticancer therapy	X	X		X
Concomitant medication and medical history	X	X		X
Efficacy (ORR, CBR, PFS, OS, DOR, TTR)	X	X	X	
Exposure	X	X		X
AEs	X	X		X
Deaths	X	X		X
Laboratory	X	X		X
Vital signs	X	X		X
ECG	X	X		X
Subgroups analyses *	X	X		X
Major protocol deviations	X	X		X

* Overview of subgroup analyses is provided in [Section 6.10](#), Subgroup Analyses and [Section 7.1](#), Adverse Events.
 Abbreviations: AE = Adverse event, DOR = Duration of response, ECG = Electrocardiogram, mTNBC = Metastatic Triple Negative Breast Cancer, ORR = Objective response rate, OS = Overall survival, PFS = Progression-free survival, TTR = Time to response.

5. STATISTICAL ANALYSES

Throughout this SAP, efficacy data will be summarized for the Target mTNBC Population, mBC, mUC, SCLC, NSCLC, CRC, EGC, EMC and PDC Population, with all patients in the respective population combined, while safety data will be summarized for the Target mTNBC Population, mBC Population, mUC Population and the Overall Safety Population. For the Overall Safety Population, data will be summarized by dose group (defined as assigned dose) and overall.

All data will be listed for the Overall Safety Population and where applicable, in the cancer-specific analysis population, as specified.

Screen failures and entered-but-not-dosed patients will be excluded from all analyses.

5.1. Patient Disposition

Disposition in terms of number of patients treated, permanently discontinued treatment, and reasons for treatment discontinuation will be summarized for the Target mTNBC Population, mBC Population, mUC Population and the Overall Safety Population.

A by-patient listing for disposition will be provided, including whether the patient is included in each of the analysis sets, treatment status, date of stopping treatment, date of stopping study participation, reason for treatment discontinuation, reason for study discontinuation, and survival follow-up status (ie, date of death, indicator of death during study, and cause of death).

Patient disposition will also be summarized for the subgroups for selected analyses populations as identified and defined in [Section 6.10](#) and [Section 7.1](#).

5.2. Demographics and Baseline Characteristics

Demographics and baseline disease characteristics for the Target mTNBC Population, mBC Population, mUC Population and the Overall Safety Population will be summarized using descriptive statistics. Continuous data will be summarized by mean, standard deviation, minimum, median, maximum and number of patients. Categorical variables will be summarized by frequency tabulations (count, percent) with a separate cell summarizing any missing data where applicable.

Individual patient listings will be provided to support the summary tables.

5.2.1. Demographics

Baseline demographic data summaries will include age, age group, sex, race, ethnicity, height, weight, body mass index (BMI), and number of subjects with renal impairment and hepatic impairment.

Patient demographic data will also be summarized for the subgroups as identified and defined in [Section 6.10](#) and [Section 7.1](#).

Age will be calculated as: Age = Integer \leq [(Informed Consent Date – Date of Birth + 1) / 365.25].

Body mass index will be calculated as: BMI (kg/m²) = weight in kg / (height in m²).

5.2.2. Baseline Disease Characteristics

Baseline disease characteristics will be provided for the target mTNBC Population, mBC Population, mUC Population and Overall Safety Population and will include Eastern Cooperative Oncology Group (ECOG) performance status, CCI [REDACTED] UGT1A1 status, tumor stage at initial diagnosis and at screening. In addition, the time since diagnosis of initial cancers will also be displayed.

5.3. Prior Anticancer Therapy

Prior systemic anticancer therapy will be summarized for the target mTNBC Population, mBC Population and mUC Population. For the Target mTNBC Population, the number of prior anticancer therapies for metastatic disease (2 prior lines vs >2 prior lines) and number of prior chemotherapies for metastatic disease (categories: 0, 1, 2, >2) will also be summarized categorically. In addition, time since last prior therapy (calculated from the end date of last prior therapy to the first dose of IMMU-132) and the duration of last line of prior therapy will be summarized. A frequency table will also be produced summarizing chemotherapy, hormonal therapy and investigational therapy products separately. For the target mTNBC Population, the number of prior anticancer therapies and of prior chemotherapies (excluding investigational and hormonal treatments) will also be summarized by the median, minimum and maximum number of therapies, and the number of patients. The number of patients receiving each individual therapy will also be summarized.

For mUC Population, the number of prior anticancer therapies, chemotherapies, cisplatin, platinum-based chemotherapies, immune check point inhibitors (CPI) including anti-PD1/PDL-1 therapies will be summarized descriptively and by categories of number of lines of each type of therapies. In addition, time since last prior therapy and the duration of last line of prior therapy will be summarized.

For mBC Population, the number of prior anticancer therapies, chemotherapies, CDK4/6 inhibitors, mTOR inhibitors, hormonal therapies, endocrine therapies, and immune CPIs will be summarized similarly descriptively and by number of lines of each type of therapies, along with summaries of time since last prior therapy and the duration of last line of prior therapy.

Additional analyses of prior anticancer therapies of particular interest, if warranted, may be generated.

